There is growing concern over the risk of over treating patients who may not be at risk of dying from the disease. Prostate cancer remains the sole malignancy where treatment is always delivered to the whole organ in routine practice. Many low risk patients therefore opt for Active Surveillance rather than immediate whole gland treatment to limit treatment related decrease in quality of life associated with either surgery or whole gland radiation. A growing body of evidence also suggests that treatment of the dominant prostatic lesion/s may be sufficient to prevent systemic disease progression, and that small lesions less than 5 mm may be indolent, thus if left untreated initially may not be likely to progress in a clinically significant manner. Additionally once a dominate lesion is treated, the patient may return to a course of active surveillance using PSA, physical examinations, and repeat MRI or biopsy as clinically indicated (Scardino 2009, Cosset 2013).

Despite early success using molecular and anatomical data to identify sub-volumes of disease for image-guided therapy, physicians remain reticent to escalate dose based upon imaging findings alone, which are inherently limited by sensitivity and specificity (Ellis 2010, Pinto 2011). Therefore, a treatment planning methodology that provided direct 3D spatial correlation of imaging sets with the gold standard of histopathology would be highly effective to exclude normal tissue (false positives by imaging) and simultaneously allow radiation dose escalation to clearly delineated “true positive” target volumes.

By using high resolution 3T MRI imaging with parametric sequencing to identify areas suspicious for harboring malignancy, we believe that focal therapy could be safely delivered to properly selected patients. Biopsy confirmation of the imaging findings for both suspicious and non-suspicious regions based on MRI imaging would be used to confirm that cancer is present at the suspected locations using a patented methodology to define the treatment target volumes. Rather than treating the whole gland, therapy could then be targeted to partial prostate volumes with the goal of reducing treatment related morbidity and long term cost for treatment.

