Standard radiotherapy for the treatment of prostate cancer is delivered at 1.8 to 2 Gy per fraction in a protracted course over 8 to 9 weeks to total doses in the range of 78 to 81 Gy. Following the published work of Hall and Brenner suggesting that prostate cancer may have a lower alpha beta ratio describing the cell line's ability to repair damage caused by ionizing radiation; many centers have routinely adopted into clinical practice that prostate cancer may be treated using larger doses per fraction ranging in size from 3 to 19 Gy in as many as 20 or as few as a single fraction of therapy (Brenner 1999). The assumption is that the alpha beta ratio of most tumors is as high as 10, while the surrounding normal tissues at risk of late radiation reactions is around 3 to 5 (Yoshioka 2013). Positive histopathology findings on co-registered diagnostic MRI data sets (T2 and parametric functional imaging) will be used to segment a dominant biologic target volume and improve disease mapping across the gland. Subjects will then be treated in a series of three SBRT (typically every other day) treatments to deliver a total dose of 29.25 Gy in 9.75 Gy fractions, yielding a total biologic equivalent dose (BED) of 273.15 allowing dose to reach the desired minimal BED of 268 with an assumed alpha beta of 1.2 for prostate cancer as suggested by Martinez (2011). A similar dose regimen has been published by Barkati et.al. using HDR brachytherapy in a three fraction dose escalation trial to deliver minimal dose of 30 Gy in 3 fractions over two days to a maximal dose of 34.5 Gy at 11.5 Gy per fraction. (Barkati 2012). While the published 3 fraction HDR regimen gave a minimal dose of 10 Gy, we feel that 9.75 Gy per fraction is effectively equivalent when taking into account the additional 12 cGy per fraction we will be giving to allow for tracking of intrafraction prostate motion with Image Guided Radiation Therapy using a series of 4 cone beam CT image sessions obtained before, during and after each fraction, thus accounting for a daily fractionated dose of 987 cGy, or 9.9 Gy. What is uniquely novel in this protocol is not the total dose of radiation delivered but rather that it is to be delivered in a non-invasive fashion using SBRT, and more importantly delivered to a novel partial prostate volume using a patented methodology to define the volume at risk to be treated using focal therapy for prostate cancer. This methodology may be adopted as a template for directing therapy to partial organ volumes using other treatment modalities based on the results of this trial if the use of tracked histopathology location is found to have significant influence on the selected treatment volumes in this study beyond what would be used based on functional and anatomic imaging studies alone.

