All clinically relevant radiologic images will be transferred to the Radiation Oncology Pinnacle (Philips, Cleveland, OH) treatment-planning system. Using the various MRI sequences and the CT image data sets, a composite gross tumor volume (GTV) will be generated. The focal GTV will be contoured and approved by the attending radiation oncologist and urologist. The 4D CT will be fused with the treatment planning CT and an internal target volume (ITV) will be generated. The location of tumor foci from each positive biopsy core will also be segmented and expanded by 5mm to add to the PTV along with imaging data sets. An additional 0.3-0.5 cm margin will be placed around the image data set ITV to generate a final PTV to account for set-up variation. The use of abdominal compression may be used to decrease the volume of ITV since there is no real-time target tracking. Surrounding normal structures, including the rectum, small bowel, bladder, femora, seminal vesicles, penile bulb, and skin will be contoured. Skin is defined as a 0.5 cm concentric ring beneath the skin.

Mid Treatment and Post SBRT (MRI) with multiparametric sequences (mpMRI)

Each subject will be offered up to 4 additional MRI scans: 1 during therapy (between the 2nd and 3rd fractionated treatments), at 6 months following the end of radiation therapy, and again at 12 and 24 months. All mpMRI will be requisitioned in the same manner as described above (Staging MRI) as described above at page 16 (6.1 Imaging the Prostate), with the exception that contrast with gadolinium is preferred. If patients are unwilling or clinically unable to undergo contrast or have all follow-up MRI scans, the patient will remain on study and followed for PSA response and toxicity outcomes.

Computed Tomography (CT)

CT will be fused with MRI scans and used as a primary image platform for treatment planning. It is preferred that CT with contrast be acquired, unless clinically contraindicated. The simulation should be performed in the supine treatment position, in the custom made immobilization device, with the fiducial markers and rectal balloon in place (where utilized). Axial cuts of 2.0 mm or less will be acquired throughout the pelvis and prostate from the top of the iliac crests superiorly to the perineum inferiorly.

Contrast

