Treatment plans from focal versus simulated whole-gland SBRT for each patient will be compared for target volume size, dose distribution, and dose reduction to organs at risk (OAR). Additional assessments for planning volumes based solely on imaging versus with correlated histopathology to define PTVs will be collected, evaluated and reported. Biological modeling will be used to evaluate tumor control probability and normal tissue complication probability (NTCP) between the two treatment paradigms (focal versus virtual simulation of whole gland treatment using conventional treatment per institutional standards). Standard independent methods of dosimetry calculations will be evaluated by Medical Physics staff and reported by Medical Physics co-investigators, utilizing such programs as Pinnacle and MUcheck, and Monte Carlo simulations. Subject data sets appropriately de-identified by a study co-author may be additionally evaluated utilizing advanced software MRI analysis for predictive modeling and comparison to tumor volume selection as identified with histopathology validation.

We estimate that 12 patients will be treated on study, and that 24 patients may be screened. MRI and histopathology data will be collected for all patients consented to the study and screened.

Interim Reports to Monitor Study Progress

Patients will have imaging sessions (MRI and CT Simulation) for treatment planning and delivery of radiation therapy. Interim imaging reports will be provided to the funding partners following the first 3-6 subjects screened, along with case study descriptions, and limited de-identified treatment plan screen shots along with composite image sets. Other interim reports will evaluate workflow and carepath processes.

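### As Target Delineation is written, histology can enlarge the PTV or leave it unchanged but not shrink it; other sections conflict with this, and the imaging-only comparison contour is not protected from knowledge of the pathology

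*Combined protocol and SAP*

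**What the plan says.** **How the volumes are built (6.1.1, Target Delineation).** "Using the various MRI sequences and the CT image data sets, a composite gross tumor volume (GTV) will be generated". An ITV follows from the 4D CT. "An additional 0.3-0.5 cm margin will be placed around the image data set ITV to generate a final PTV". For histology: "The location of tumor foci from each positive biopsy core will also be segmented and expanded by 5mm to add to the PTV". Negative cores are given no role in this section.

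**What is compared (9.1, dosimetric and biological advantage).** "Additional assessments for planning volumes based solely on imaging versus with correlated histopathology to define PTVs will be collected, evaluated and reported". No metric, direction, test or threshold is named.

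**What the comparison is for (1.2 Background).** Histological correlation is justified as a way to "exclude normal tissue (false positives by imaging") and to escalate dose to true positives. The method may serve as a template for other treatments "if the use of tracked histopathology location is found to have significant influence on the selected treatment volumes in this study", beyond what imaging alone would give.

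**Other text on which foci count.**
- 1.2 also says that positive histology on co-registered MRI will be used to segment the dominant target.
- 6.0 allows one or two dominant foci on the screening MRI.
- 9.2 (Target lesions) allows one biopsy-positive lesion to be selected for focal therapy.
- 9.2 (non-target table) covers foci under 5 mm or with under 5% of the biopsy tissue involved, whereas 6.1.1 adds every positive core.

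**Timing (7.2 and 7.3).** Guided biopsy is visit 2. Planning MRI and CT are visit 3, two to three weeks after fiducial placement.

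**The concern.** There are two separate problems.

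**The written rule is additive.** If the histology-informed PTV is the imaging PTV plus expanded positive cores, a man's difference is zero or positive. The comparison can then show cancer that imaging missed. It cannot show normal tissue that histology spared, although sparing is the reason Section 1.2 gives for the method. Other sections point to a different construction, so an analyst could not tell which volume to compute.

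**The comparator is not protected.** Nothing says when, or by whom, the imaging-only volume is drawn. The mapping biopsies help decide eligibility (6.1.1), so visit 2 pathology should be available when planning starts. A contourer who knows it may extend the imaging contour to cover a known positive site, which hides added volume. He or she may instead leave out an equivocal area known to be negative, which hides removed volume, or draw the imaging contour more narrowly than otherwise, which inflates added volume.

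At stake is the estimate of how much tracked histology changes the target, on which Section 1.2 rests possible wider adoption.

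**Working it through.** The plan gives no sample size, effect or threshold for this comparison, so there is no figure to reproduce. The check is one of logic, with illustrative numbers.

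**1. Sign of the difference under 6.1.1.** Let A be the imaging PTV and C the positive-core foci expanded by 5 mm. The histology-informed PTV is A ∪ C, so V(A ∪ C) − V(A) ≥ 0. It is never negative.

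**2. When it is zero.** If a focus lies inside the GTV and the margin is 5 mm, its 5 mm expansion lies inside A, so the added volume is 0.00 cc.

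With a 3 mm margin, take a spherical lesion, no ITV motion and a point focus (assumptions). A central core adds 0.00 cc. A core on the lesion edge adds 0.524 cc minus the overlap of two spheres:

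overlap = π(R+r−d)²(d²+2dr−3r²+2dR+6rR−3R²)/(12d), with r = 5 mm, R = lesion radius + 3 mm, d = lesion radius.

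- 6 mm lesion (R = 6, d = 3): 0.524 − 0.402 = 0.12 cc.
- 15 mm lesion (R = 10.5, d = 7.5): 0.524 − 0.442 = 0.08 cc.

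**3. Largest addition from one focus.** A 5 mm sphere wholly outside A adds 4/3 × π × 0.5³ = 0.524 cc. Relative to a spherical imaging PTV this is (5/R)³:

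| Lesion | Margin | Imaging PTV | Added |
|---|---|---|---|
| 10 mm | 5 mm (R = 10) | 4.19 cc | 12.5% |
| 10 mm | 3 mm (R = 8) | 2.14 cc | 24% |
| 6 mm | 5 mm (R = 8) | 2.14 cc | 24% |
| 6 mm | 3 mm (R = 6) | 0.90 cc | 58% |

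**4. Size of the conflict between sections.** Take two separate 10 mm MRI foci, one biopsy-positive at its centre and one biopsy-negative.

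| Rule | 3 mm margin | 5 mm margin |
|---|---|---|
| Imaging only | 2 × 2.14 = 4.29 cc | 2 × 4.19 = 8.38 cc |
| 6.1.1 as written | 4.29 cc (no change) | 8.38 cc (no change) |
| 9.2, only the biopsy-positive lesion | 2.14 cc (−50%) | 4.19 cc (−50%) |

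(4.29 is twice the unrounded 2.145.) The same man contributes no change or a halving, depending on which section the analyst follows.

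**5. Why a test against zero would say little.** If no difference can be negative, k men with any added volume give a two-sided sign-test p of 2 × 0.5^k: 0.031 for k = 6 and 0.008 for k = 8. These are illustrative only, since no test is planned and the documents give no basis for any k.

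**6. Precision of a descriptive report with 12 men.** Exact 95% intervals are 0% to 26.5% for 0 of 12 and 5.5% to 57.2% for 3 of 12.

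**The case against.** The strongest reply is that a reader who infers that the comparison can come out only one way, and so cannot test the trial's claim, goes too far.

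- **Volume can fall under other text.** 9.2 with 6.0, and the segmentation sentence in 1.2, allow a biopsy-negative MRI focus to be dropped. This stands. It turns the point into a conflict between sections. The 9.2 rule sits among the response definitions, and Target Delineation does not apply it.
- **Size can still be informative.** Zero change is possible, and a material addition needs proven cancer outside the imaging PTV. That is the non-directional influence Section 1.2 asks about. This stands, provided that the imaging-only contour was drawn without the pathology.
- **False positives are studied elsewhere.** A reader might infer that they cannot be observed at all. The first aim in 2.0 and the MRI-biopsy analyses in 9.0 and 10.2 examine them, and 9.1 collects these data for all screened men. What those analyses do not measure is the effect on treated volume.
- **No test is planned.** 9.1 promises a report, and the adoption remark is Background without a threshold. This stands, so the p-values carry no weight as a criticism.
- **Foci wholly outside the imaging PTV may be uncommon.** 4.3 requires a single dominant lesion, and the mapping biopsies look for multifocal disease. This stands; the 12.5% to 58% range applies only to such foci.
- **An early lock is imperfect.** The full PTV needs the visit 3 4D CT, and men with an earlier targeted biopsy (6.1.1) already have pathology. Both are true, and the fix is limited accordingly.

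**Conclusion.** The point holds in limited form and is a cheap improvement rather than a flaw that invalidates the study. Under Target Delineation alone, histology leaves the PTV unchanged or enlarges it, so the 9.1 comparison cannot show imaging false positives being kept out of the treated volume. Sections 1.2, 6.0 and 9.2 imply otherwise. For two equal, separate MRI foci with one biopsy-negative, the gap between the readings is half the imaging volume. Separately, the imaging-only volume may be drawn with visit 2 pathology known, which biases the estimated influence in an unknown direction and by an amount the documents do not allow one to calculate.

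The volume figures assume spheres, no ITV motion and point foci. The conclusion on sign needs only the additive rule. The conclusion on bias needs only the visit order and the absence of any contouring rule.

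**What to change.** In Section 9.1:

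1. Have the same physician contour and lock the imaging-only GTV on the staging MRI before visit 2 pathology is released. Carry it by registration to the planning scan, then apply the same ITV and PTV margins as for the histology-informed volume.
2. Report added, removed and overlapping volume for each man.
3. Give exact 95% intervals, with stated denominators, for the proportion of men with a positive core outside the imaging-only PTV and the proportion with an MRI-suspicious focus whose cores were all negative.
4. Describe size; do not test the volume difference against zero.
5. Report men with a prior targeted biopsy separately, because their pathology was already known.

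Sections 1.2, 6.0, 6.1.1 and 9.2 must be reconciled on how biopsy-negative MRI regions and low-volume positive cores enter each comparison volume. No target rule is proposed here.

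**Cost.** Protocol wording and one earlier contour per man. Because eligibility depends partly on the visit 2 biopsy, this may mean up to the 24 men screened for the 12 treated. Registration between staging and planning scans adds some error to the comparison. The lock protects only against visit 2 pathology; each man's positive diagnostic biopsy comes earlier.

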7.2 Study Visits

Biopsy and Fiducial Placement – visit #2

- Weight
- Vitals including blood pressure, pulse, respiratory rate, temperature
- Physical examination
- Guided biopsy
- Fiducial placement

MRI and CT scans for RT SIM – visit #3

- RT CT (with contrast unless contraindicated) for simulation
- Pelvic MRI with Contrast
- Pelvic CT for SIM

SBRT #1 – visit #4

- RT treatment

SBRT #2 – visit #5

- RT treatment

MRI – visit #6

- Pelvic mpMRI with Contrast

SBRT #3 – visit #7

- Adverse events assessment (may be completed by telephone call within 7 days post visit 7)
- RT treatment

Follow up, every 3 months for up to 24 months – visits #8 - #16

- Weight
- Vitals including blood pressure, pulse, respiratory rate, temperature
- Physical examination
- ECOG performance status
- Quality of life Score standard of care IPSS and SHIM Scores
- Adverse events assessment

Post SBRT Follow up Measurements

- PSA to be completed at ALL follow up visits

- DRE to be completed at **ALL** follow up visits
- Serum Creatinine and BUN Blood Draw at **6, 12, and 24** months follow up prior to MRI
- Pelvic MRI to be completed at **6, 12, and 24** month follow up visits with contrast
- EPIC EQ D5, Sexual Medication/Device screening to be completed at **6, 12 and 24** months

Any positive results for staging Post RT (positive digital rectal exam or evidence of biochemical failure using the clinical nadir +2 definition (serum PSA rise above 2ng/mL from the post therapy nadir (Phoenix, Abramowitz 2007) may trigger clinical indication for SOC staging MRI to rule out disease progression. If acquired, this data will be collected for comparison to other serial MRI data. Should a patient be deemed to have failed therapy using the Phoenix criteria (nadir +2ng/mL PSA) the subject/s will be referred for consultation for review of options for salvage therapy, and if the patient elects a second treatment the subject will be taken off study.

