7.3 Study Calendar

Study Days	Screen Visit 1	Biopsy and Fiducial Placement Visit 2	MRI* & CT Scans for RT SIM Visit 3	SBRT #1 Visit 4	SBRT #2 Visit 5	MRI Visit 6	SBRT #3 Visit 7	30 days post RT Visit 8	3 mo post RT Visit 9	6 mo post RT Visit 10	9 mo post RT Visit 11	12 mo post RT Visit 12	15, 18 & 21 months post RT Visits 13-15	24 mo Post RT Visit 16
REQUIRED ASSESSMENTS			2-3 wks Post Fiducials	2-3 wks Post SIM										
Informed Consent	X													
Demographics	X													
Medical History	X													
Height	X													
Weight	X	X						X	X	X	X	X	X	X
Vitals (BP Respiration Pulse Temp)	X	X						X	X	X	X	X	X	X
Physical Examination	X	X						X	X	X	X	X	X	X
Concomitant medication assessment including hormone therapy	X							X	X	X	X	X	X	X
ECOG PS	X							X	X	X	X	X	X	X
Baseline Symptoms	X													
IPSS/SHIM QoL Scores	X							Xa	Xa	Xa	Xa	Xa	Xa	Xa
Adverse Event Assessment							X ²	X	X	X	X	X	X	X
CBC w diff /platelets /testosterone	X													
Serum Chemistry ¹	X													
Guided biopsy		X												
Fiducial placement		X												
RT simulation			X											
RT TREATMENT				X	X		X							

Study Days	Screen Visit 1	Biopsy and Fiducial Placement Visit 2	MRI* & CT Scans for RT SIM Visit 3	SBRT #1 Visit 4	SBRT #2 Visit 5	MRI Visit 6	SBRT #3 Visit 7	30 days post RT Visit 8	3 mo post RT Visit 9	6 mo post RT Visit 10	9 mo post RT Visit 11	12 mo post RT Visit 12	15, 18 & 21 months post RT Visits 13-15	24 mo Post RT Visit 16
DISEASE ASSESSMENT														
Pelvic MRI *	X ^{3,4}		X*			X*			X*		X*			X*
Pelvic CT for SIM			X*											
Bone Scan	X ⁴													
PSA	X ⁴								X	X	X	X	X	X
DRE	X ⁴								X	X	X	X	X	X
EPIC EQ D5, Sexual Medication, Device Screening	X									X		X		X

1: Albumin, alkaline phosphatase, total bilirubin, bicarbonate, BUN, calcium, chloride, creatinine, glucose, potassium, total protein, SGOT [AST], SGPT [ALT], sodium. Calculated creatinine clearance will be done if creatinine and/or BUN are abnormal

2: Post treatment A/E assessment may be a telephone call within 7 days post end of therapy.

3: SOC Staging MRI

4: Must have been completed within 90 days of screening visit

a: Physician or Nurse Practitioner consult at post RT visits

* Serum Creatinine And BUN Blood Draw performed prior to pelvic MRI with contrast (mandatory for eligibility)per institutional guidelines.

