Evaluable Non-Target Disease Response Patients who have lesions present at baseline that are evaluable, but do not meet the definitions of measurable disease, have completed a course of SBRT, and have had their disease re-evaluated by imaging will be considered evaluable for non-target disease. The response assessment is based on the presence, absence, or unequivocal progression of the lesions.

Disease Parameters

Radiologic Surveillance

Standard of care follow-up post RT will include contrast enhanced MRI and parametric imaging unless clinically contraindicated should include contrast.

Measurement of Response

Measurement of Response Prior to Study Entry

The revised RECIST guideline, v. 1.1. [European J of Cancer. 45: 228-247, 2009] will be used as applicable to the protocol. See

http://ctep.info.nih.gov/protocolDevelopment/docs/recist_guideline.pdf for further details.

Additional definitions beyond the RECIST guidelines specific to this protocol are incorporated to define local control as described below (Eisenhauer 2009). We will evaluate and report RECIST measures minimally at 12 and 24 months post radiation therapy.

Response Criteria: Evaluation of Target Lesions

Complete Response (CR): Disappearance of all target lesions

Partial Response (PR): At least a 30% decrease in the sum of the diameters of target lesions taking as reference the baseline sum diameters

Progressive Disease (PD): At least a 20% increase in the sum of diameters of target lesions, taking as reference the smallest sum on study (includes the baseline sum if that is the smallest on study). The sum must also demonstrate an absolute increase of at least 5 mm. The appearance of new lesion(s).

Stable Disease (SD): Neither sufficient shrinkage to qualify for PR nor sufficient increase to qualify for PD, taking the smallest sum diameters as reference while on study.

3D Lesion Volumes

In addition to RECIST criteria evaluation on follow-up scans, we will report 3 D volumetric data of individual lesions based on pre and post treatment images over time, for comparison to 2 D RECIST measurements (Guio 2012 and Eisenhauer 2009).

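### The study calendar places follow-up pelvic MRI at 3, 9 and 24 months where the text sets 6, 12 and 24, so the calendar schedules no scan for the 12-month RECIST report

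*Combined protocol and SAP*

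**What the plan says.** Three parts of the combined protocol and SAP bear on when follow-up MRI is done.

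- **Text.** Section 6.1.1, on mid-treatment and post-SBRT MRI, states: "Each subject will be offered up to 4 additional MRI scans: 1 during therapy". The other three fall "at 6 months following the end of radiation therapy, and again at 12 and 24 months". Section 7.2 words it as a requirement: "Pelvic MRI to be completed at 6, 12, and 24 month follow up visits with contrast". It also sets the blood tests to match: "Serum Creatinine and BUN Blood Draw at 6, 12, and 24 months follow up prior to MRI".
- **Calendar.** In section 7.3 the relevant column headings run "3 mo post RT Visit 9 6 mo post RT Visit 10 9 mo post RT Visit 11 12 mo post RT Visit 12", followed by one column for 15, 18 and 21 months and one for 24 months. The imaging row reads "Pelvic MRI * X ^{3,4} X* X* X* X* X". The blank cells between marks do not show in that quotation; their positions are set out in the working.
- **Reporting.** Section 9.2 commits to a minimum: "We will evaluate and report RECIST measures minimally at 12 and 24 months post radiation therapy". It also plans 3D lesion volumes from scans before and after treatment, without naming a month. Section 10.2 tests volume before against after treatment, again without a month, and calls the RECIST and volumetric reports descriptive.

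**The concern.** The calendar and the text agree on only one of the three follow-up MRI times. Followed literally, the calendar produces no scheduled 12-month scan, although 12 months is one of the two times at which RECIST must be reported. A 12-month scan that is not taken cannot be recovered later.

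Scan timing also affects dated events. Section 10.2 plans Kaplan-Meier curves for radiographic efficacy, including time to local progression, and section 9.1 estimates disease-free survival at 6, 12 and 24 months. Progression seen on MRI can be dated only when a scan is done. Under the calendar the last scheduled gap is 24 − 9 = 15 months; under the text it is 24 − 12 = 12 months. If some men are scanned by the text and others by the calendar, scans from different times are pooled, and in a series of 12 that cannot be averaged away.

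**Working it through.** No power or alpha figure is involved. The check is to map each mark in the calendar to its column and compare it with the text.

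**Step 1: columns.** The header has 15 cells: one label and 14 visit columns. Columns 1 to 12 are Visits 1 to 12, column 13 is Visits 13–15, and column 14 is Visit 16.

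**Step 2: MRI row.** It also has 15 cells. The marks fall in columns 1, 3, 6, 9, 11 and 14.

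| Time point | Text (6.1.1, 7.2) | Calendar MRI row (7.3) | RECIST minimum (9.2) |
|---|---|---|---|
| Between fractions 2 and 3 (Visit 6) | yes | yes | – |
| 3 months (Visit 9) | no | **yes** | – |
| 6 months (Visit 10) | yes | **no** | – |
| 9 months (Visit 11) | no | **yes** | – |
| 12 months (Visit 12) | yes | **no** | yes |
| 24 months (Visit 16) | yes | yes | yes |

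**Step 3: is the whole table shifted?** Eight other rows were mapped in the same way, and each has 15 cells. The quality-of-life row, "EPIC EQ D5, Sexual Medication, Device Screening X X X X", falls at screening, 6, 12 and 24 months, as the text says. Radiation treatment falls at Visits 4, 5 and 7, and simulation at Visit 3. PSA and DRE run from 3 months onward. The columns as a whole are therefore not displaced. Within the MRI row itself, the screening, simulation, mid-treatment and 24-month marks are where they should be.

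**Step 4: number of scans.** The calendar has 1 mid-treatment mark and 3 follow-up marks, and 1 + 3 = 4, which matches the number offered in 6.1.1. The count agrees; only the timing differs.

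**Step 5: size.**
- Follow-up times that agree: 1 of 3 (24 months).
- RECIST minimum times with a calendar scan: 1 of 2 (24 months).
- Offered follow-up scans: 12 men × 3 = 36.
- Scans displaced if every man accepts every scan and every order follows the calendar: 12 × 2 = 24 of 36.
- Displacement: 6 − 3 = 3 months and 12 − 9 = 3 months, both early.
- Men with a 12-month MRI scheduled by the calendar: 0 of 12.

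**Step 6: does a visit window close the gap?** Section 7.0 gives a window of 2–3 with no time unit, so it does not establish that a 9-month scan could count as the 12-month one.

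**The case against.** The strongest objection is that the mismatch may come from the PDF reading. Moving just the two disputed marks one column to the right gives exactly 6, 12 and 24 months. One blank cell lost before the pair and one gained after it would leave the row at 15 cells with its outer marks correct. The sound quality-of-life row shows that the header is right; it does not show that this row is. The PSA row is also an imperfect control: section 7.2 asks for PSA at all follow-up visits, yet the calendar leaves Visit 8 blank, although the three-monthly schedule in 10.2 fits. This stands as a reason to check the original page before amending anything.

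It is also fair to say that the harm is not demonstrated. The study is at one institution, the text gives the months plainly in two sections, and the OnCore calendar that section 13.0 mentions is not available here. Nothing in the documents says which source staff schedule from.

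Four stronger readings are tempting, and the documents do not support them:

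- *A 12-month volume endpoint is lost.* Only RECIST is tied to 12 months. Volumes have no stated month and lose the point only because they use the same scans.
- *Scans at 3 and 9 months would go without renal function tests.* The asterisk footnote to the calendar attaches the creatinine and BUN draw to each contrast MRI, so the draw would follow the scan.
- *24 of 36 scans will be mistimed.* That is a ceiling. Section 6.1.1 offers the scans and keeps men on study if they do not have them all.
- *The main endpoints are compromised.* The EPIC co-primary endpoints and the toxicity goal do not depend on MRI timing. Serial MRI does contribute to the efficacy assessment in section 9.0, but RECIST is reported descriptively, and the sample-size section disclaims adequate power for clinical outcomes.

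The tolerance for missed scans does not remove the point. A man declining a scan is different from a calendar that never schedules it, and 7.2 says the scan is to be completed.

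**Conclusion.** The inconsistency holds as the calendar is extracted. Two of three follow-up MRI times in 7.3 differ from 6.1.1 and 7.2, each by 3 months, and the calendar schedules no scan for one of the two RECIST reporting times in 9.2. The effect is at most 24 of 36 offered follow-up scans, and it can be none if staff schedule from the text. Kaplan-Meier analyses can use actual scan dates, and PSA- or DRE-triggered MRI may add scans, so the loss falls mainly on the 12-month RECIST report.

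The conclusion assumes that the extracted row reproduces the original page and that at least some scans are ordered from the calendar. On that footing it is an internal inconsistency, wrong as written, that should be fixed. It does not call the study's main quality-of-life or toxicity results into question.

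**What to change.** 1. Check the Pelvic MRI row of 7.3 against the original page.
2. If the marks are as extracted, reconcile the row with 6.1.1, 7.2 and 9.2 by placing the follow-up marks at Visit 10 (6 months), Visit 12 (12 months) and Visit 16 (24 months).
3. Check the OnCore calendar of events against the corrected row.
4. For any scan already taken at 3 or 9 months, record and analyse it by its actual date. Do not relabel it as a 6- or 12-month scan, and report how many men have a true 12-month scan.

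No separate creatinine or BUN entry is needed, because the existing footnote moves with the MRI marks. The cost is a one-row amendment and a check of the OnCore schedule. The number of scans per man does not change.
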